5.2 Primary Efficacy Endpoint(s)

5.2.1 Definitions

Six-point ordinal clinical recovery scale

The 6-point ordinal clinical recovery scale (CRS) provides 6 mutually exclusive conditions ordered from best to worst, and the score reflects the participant's worst situation on the day of the assessment:

1. Not hospitalized
2. Hospitalized, not requiring supplemental oxygen
3. Hospitalized, requiring low flow supplemental oxygen
4. Hospitalized, on non-invasive ventilation, nonrebreather mask or high flow oxygen device
5. Hospitalized, on IMV or ECMO
6. Death

The CRS can be derived from baseline up to and including day 28. The CRS will be missing after trial discontinuation if the participant discontinued the trial for other reason than death. Participants who die before day 28 (before or after discharge from hospital) will be considered to continue the trial up to and including day 28.

The CRS categories are defined below. For ease of categorization, the categories are defined from worst to best. A participant will be evaluated in the same ordering of the categories as below. Once a participant fulfils the criteria for a category, the category is assigned to the participant and the evaluation stops.

6. Death
 - o Participant died at any time on the day of assessment or earlier (all-cause mortality).
5. Hospitalized, on IMV or ECMO

- o IMV or ECMO is used at any time on the day of assessment, OR
- o From a Medical Perspective, the participant should have been on IMV on the day of the assessment

4. Hospitalized, on non-invasive ventilation, nonrebreather mask, or high flow oxygen device
 - o The participant is on supplemental oxygen and the worst FiO₂ is $\geq 50\%$.
3. Hospitalized, requiring low flow supplemental oxygen
 - o On supplemental oxygen with worst FiO₂ $< 50\%$ and the participant was not able to sustain a blood oxygen saturation of $> 93\%$ when breathing room air, OR
 - o Not on supplemental oxygen and the minimum of all available SpO₂ values during the day is $\leq 93\%$
2. Hospitalization, not requiring supplemental oxygen
 - o Hospitalized according to the status described below
1. Not hospitalized, including subjects on low level of oxygen

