 - o A distinction will be made between subjects discharged and in need of (score 1.2) or not in need of (score 1.1) oxygen supplementation as indicated by the investigator on the discharge questionnaire. This distinction will not be made when calculating improvements on the CRS, for which score 1 will be used in both cases.

Hospitalization status

The hospitalization status considered for the definition of the CSR will be defined according to the rules described below. The hospitalization status will be evaluated in the same ordering of rules. Once a participant fulfils the criteria, the hospitalization status is defined and the evaluation stops.

1. If a participant is discharged to the alternate care settings ‘different hospital’, ‘acute care facility’, ‘subacute care facility’ or ‘hospice/palliative discharge’, the participant will be considered hospitalized until day 28 or trial discontinuation, whichever comes first. The participant will be categorized in the category the participant was in at time of discharge until trial discontinuation.
2. If a participant is discharged ‘against medical advice’, the participant will be considered hospitalized on the day of discharge and on the day after discharge, unless the participant discontinued the trial. The participant will be categorized in the category the participant was in at time of discharge. The CRS will be considered missing from 2 days after discharge onwards.
3. If a participant is hospitalized although ‘ready for discharge’ according to the investigator, the participant will be considered hospitalized up to and including the first day on which the participant was considered ready for discharge. The participant will be considered “Not hospitalized” from the day after until day 28 or trial discontinuation, whichever comes first (unless the status changes back to “not ready for discharge”).
4. If a participant is discharged although ‘not ready for discharge’ according to the investigator, the participant will be considered hospitalized up to and including 1 day

after the day of discharge, unless the participant discontinued the trial. The participant will be categorized in the category the participant was in at time of discharge. The participant will be considered non hospitalized from 2 days after the day of discharge onwards until day 28 or trial discontinuation, whichever comes first.

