5. If a participant is discharged from the hospital, the day of discharge will be considered as “hospitalized”. The participant will be categorized in the category the participant was in at time of discharge. After this day, the participant will be considered “Not hospitalized” until day 28 or trial discontinuation, whichever comes first.

Baseline

The 6-point ordinal CRS at the time of randomization request will be used as the baseline. If the baseline assessment of the CRS is missing, the first available assessment within 12 hours after randomization will be used. If the latter is also missing, the last available assessment prior to baseline will be used.

Sustained Clinical Improvement

Clinical Improvement is obtained if the score on the CRS improved with at least 2 categories with respect to the baseline score.

Sustained clinical improvement is defined as a clinical improvement without documented loss of this clinical improvement up to and including day 28 or until trial discontinuation, whichever comes first.

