5.2.3 Analysis Methods

All participants for which the trial is still ongoing at Day 28 and without sustained clinical improvement by Day 28 will be censored on Day 28. Participants that discontinue the study before day 28 will be censored at the last assessment of the CRS, unless they had an event of sustained clinical improvement prior to discontinuation. Participants that died at day 28 or earlier will be censored at day 28, irrespective of whether a clinical improvement occurred prior to death.

The primary hypothesis of this study is that Sirukumab in combination with SOC results in a statistically significant shorter time to sustained improvement (defined as an improvement of at least 2 categories relative to baseline on the 6-point ordinal CRS) versus placebo in combination with SOC, in participants with confirmed critical COVID-19.

The primary hypothesis will be evaluated based on the Logrank test, stratified for the stratification factors (age [<65 and ≥ 65 years] and use of IMV [yes/no]). This test will be performed 2-sided at a 5% significance level. The actual values of the stratification factors will be used, not as randomized.

The hazard ratio of sustained clinical improvement for experimental treatment versus placebo, from baseline until day 28 will be considered as the population-level summary measure of the treatment effect for the primary estimand. The hazard ratio will be estimated in a Cox proportional hazards model stratified for the stratification factors and with treatment as a single covariate. A value larger than 1 indicates the chance of improvement is larger in the experimental treatment group. The 95% Wald confidence interval will be added.

The Log-rank test might generate a different p-value compared to that of the Wald test of the hazard ratio. The Logrank test will be used for formal inference (and not the Wald p-value or CI from the hazard ratio).

Cumulative proportion of patients with clinical improvement, by treatment, will be provided using the complement of the Kaplan Meier curve. The analyses will be completed with the median time to clinical improvement (if reached) and the proportion of participants who had their clinical improvement on day 7, 14, 21 and 28; all per Kaplan Meier method. The complementary log-log transform method is used to calculate the 95% confidence intervals.

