5.3.2 Key Secondary Estimands

Clinical improvement at Day 28

Population: The population of interest are hospitalized patients between ≥ 18 and <85 years old with confirmed critical COVID-19 disease.

Endpoint: Sustained clinical improvement at Day 28 (yes/no)

Interventions: Received Sirukumab 5 mg/kg (IV single dose infusion on Day 1) and placebo (IV infusion on Day 1), both on top of SOC.

Intercurrent Events:

- Death as intercurrent event is handled in a composite strategy as it is the worst category on the clinical scale. Participants that died at Day 28 or earlier will be considered as failure (Sustained clinical improvement at Day 28=no), irrespective of whether a clinical improvement occurred prior to death.
- The intercurrent event of the use of prohibited medication is handled in a treatment policy strategy: data will be used as observed.
- The intercurrent event of discharge to the alternate care settings ‘different hospital’, ‘acute care facility’, ‘subacute care facility’ or ‘hospice/palliative discharge’ is handled in a while on treatment strategy: see section 5.2.1
- Participants that discontinue the study before Day 28 will be considered as failure (Sustained clinical improvement at Day 28=no), unless they had an event of sustained clinical improvement prior to discontinuation. In the latter scenario it will be considered a success (Sustained clinical improvement at day 28=yes).

Population-level summary measure:

The difference in proportion of participants with of ‘Sustained clinical improvement at Day 28’ for experimental treatment versus placebo.

All-cause mortality up to Day 28

Population: The population of interest are hospitalized patients between ≥ 18 and <85 years old with confirmed critical COVID-19 disease.

Endpoint: Death by Day 28 (Yes/No)

Treatment: Sirukumab 5 mg/kg (IV single dose infusion on Day 1) and placebo (IV infusion on Day 1), both on top of SOC.

Intercurrent events:

- The intercurrent event of the use of prohibited medication is handled in a treatment policy strategy: data will be used as observed.
- Participants that discontinue the study before Day 28 with a score > 1 on the CRS will be analyzed according to the composite strategy and will be considered as death on day 28 (Death by day 28=yes).

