| Against medical advice? | | | | YES | | |
| Status (SS*) | hospitalized | hospitalized | hospitalized | Discharged | | |
| Discharge to** | | | | 1/5/.. | | |
| ready (SS*) | --/Not ready | --/Not ready | --/Not ready | --/Ready/ Not ready | | |
| CRS | >1 | >1 | >1 | >1 | >1 | Missing |

*SS = Subject Status

1= not hospitalized; > 1 = hospitalized

** 1=Patient's Home; 2=Different Hospital; 3=Acute Care Facility; 4=Subacute care facility

5=Long-Term Facility; 6=Rehab Facility; 7=Hospice/Palliative Discharge; 8=Other

Case 4: Ready for discharge at Day 5 (rule 3)

| Case 4 | Day 3 | Day 4 | Day 5 | Day 6 | Day 7 | Day 8 to Day 28 |
|----------------------------|--------------|--------------|--------------|--------------|------------|-----------------|
| Against medical advice? | | | | | --/NO | |
| Status (SS*) | hospitalized | hospitalized | hospitalized | hospitalized | Discharged | |
| Discharge to** ready (SS*) | --/Not ready | --/Not ready | Ready | --/Ready | 1/5/.. | |
| CRS | >1 | >1 | >1 | 1 | --/Ready | 1 |

Case 5: Discharged from hospital on Day 6, but not ready for discharge (Rule 4)

| Case 5 | Day 3 | Day 4 | Day 5 | Day 6 | Day 7 | Day 8 to Day 28 |
|-----------------------------|--------------|--------------|--------------|------------|--------|-----------------|
| Against medical advice? | | | | --/NO | | |
| Status (SS*) | hospitalized | hospitalized | hospitalized | Discharged | | |
| Discharged to** ready (SS*) | --/Not ready | --/Not ready | --/Not ready | Not ready | 1/5/.. | |
| CRS | >1 | >1 | >1 | >1 | >1 | 1 |

Case 6: Ready for discharge at Day 5, Not ready for discharge at Day 6 (rule 3)**Discharged from hospital on Day 7 (Rule 5)**

| Case 6 | Day 3 | Day 4 | Day 5 | Day 6 | Day 7 | Day 8 to Day 28 |
|----------------------------|--------------|--------------|--------------|--------------|------------|-----------------|
| Against medical advice? | | | | --/NO | | |
| Status (SS*) | hospitalized | hospitalized | hospitalized | hospitalized | Discharged | |
| Discharge to** ready (SS*) | --/Not ready | --/Not ready | Ready | Not ready | 1/5/.. | |
| CRS | >1 | >1 | >1 | >1 | >1 | 1 |

*SS = Subject Status

1= not hospitalized; > 1 = hospitalized

** 1=Patient's Home; 2=Different Hospital; 3=Acute Care Facility; 4=Subacute care facility

5=Long-Term Facility; 6=Rehab Facility; 7=Hospice/Palliative Discharge; 8=Other

Case 7: Ready for discharge at Day 4, Not ready for discharge at Day 5 (rule 3)

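### Discharge to hospice or palliative care freezes the recovery category, so a two-category gain already held at that discharge counts as sustained improvement unless a death by Day 28 is recorded

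*SAP*

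**What the plan says.** SAP 5.2.1 sets out hospitalization-status rules that are applied in order. Rule 1 covers discharge to a different hospital, an acute or subacute care facility, or hospice/palliative care. For all of these, "the participant will be considered hospitalized until day 28 or trial discontinuation, whichever comes first". On the category it adds: "The participant will be categorized in the category the participant was in at time of discharge until trial discontinuation". Attachment 3 repeats the rule and lists the discharge destinations, ending "5=Long-Term Facility; 6=Rehab Facility; 7=Hospice/Palliative Discharge; 8=Other"; the patient's home is code 1.

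Improvement means a gain of at least two categories from baseline. It is sustained when it holds "without documented loss of this clinical improvement up to and including day 28 or until trial discontinuation".

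Death is handled separately and takes precedence. Category 6 is checked first, and SAP 5.2.1 states: "Participants who die before day 28 (before or after discharge from hospital) will be considered to continue the trial up to and including day 28". SAP 5.2.3 adds: "Participants that died at day 28 or earlier will be censored at day 28, irrespective of whether a clinical improvement occurred prior to death". SAP 5.3.2 treats death as failure in the Day 28 improvement key secondary in the same way.

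The estimand sections (5.2.2 and 5.3.2) label discharge to any of the rule 1 settings a while-on-treatment strategy.

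**The concern.** Moving to another acute hospital and entering hospice mean different things for prognosis, but rule 1 scores them alike. After a hospice discharge the category no longer reflects what happens to the participant. Any deterioration short of death is invisible, because the carried-forward category cannot show it. A gain held on the day of discharge therefore becomes a sustained gain by construction.

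The while-on-treatment label does not explain this. Treatment is a single Day 1 infusion, so what the rule does is carry the last observation forward. Protocol 8.1.1 counts alternate settings as hospital when they deliver care normally given in a hospital. It does not name hospice; the SAP adds it.

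What is at stake is the meaning of a success on the primary endpoint and on the first key secondary. With 37 and 74 participants planned per arm, a few misclassified cases are visible in the rates.

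**Working it through.** **1. The plan's own figure.** Inputs from SAP 1.4: 37 control and 74 sirukumab; log-normal time to improvement in survivors with medians 28 and 16.8 days and SD 0.9; mortality 40% and 20%; deaths and non-improvers censored at Day 28.

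- Control improvement by Day 28: 0.60 × Φ(0) = 0.60 × 0.50 = 30.0%.
- Sirukumab: 0.80 × Φ(ln(28/16.8)/0.9) = 0.80 × Φ(0.568) = 57.2% (the SAP targets 55%).
- Simulated unstratified two-sided log-rank power, 4000 runs: 0.82 in continuous time and 0.81 in whole days. The stated power of at least 80% reproduces.
- Key secondary improvement, 30% against 55%, one-sided 5%: power 0.814. This also agrees.

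**2. Walking the rules.** Take baseline 4 or 5, a category of 2 to 5 at hospice discharge, and three outcomes: death by Day 28 recorded, alive at Day 28, or discontinued with any death unrecorded. That gives 2 × 4 × 3 = 24 paths.

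| Baseline | Category at hospice discharge | Death by Day 28 recorded | Alive at Day 28 | Discontinued, death unrecorded |
|---|---|---|---|---|
| 4 | 2 | no event | event | event |
| 4 | 3, 4 or 5 | no event | no event | no event |
| 5 | 2 or 3 | no event | event | event |
| 5 | 4 or 5 | no event | no event | no event |

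All 8 recorded-death paths give no event. Of the other 16, 6 give an event: three baseline-and-category pairs, each with two outcomes.

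**3. What one case is worth.** 1/37 = 2.7 percentage points in control; 1/74 = 1.4 points in sirukumab.

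**4. Illustration of size.** The documents give no hospice rate, so this is an assumed range. Some fraction of participants who are alive at Day 28 and would not otherwise improve is scored as an event on a random day from 5 to 27. Under the design assumptions that pool is 37 × 0.60 × 0.50 = 11.1 in control and 74 × (0.80 − 0.572) = 16.9 in sirukumab. Whole-day times, 3000 runs per changed scenario.

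| Assumed fraction | Extra events, control / sirukumab | Log-rank power |
|---|---|---|
| none | 0 / 0 | 0.81 |
| 5% in both arms | 0.6 / 0.8 | 0.80 |
| 10% in both arms | 1.1 / 1.7 | 0.78 |
| 20% in both arms | 2.2 / 3.4 | 0.76 |
| 20% in control only | 2.2 / 0 | 0.60 |
| 20% in sirukumab only | 0 / 3.4 | 0.91 |

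The simulation error is about √(0.8 × 0.2/3000) = 0.007, so 0.80 is barely distinguishable from 0.81. With no treatment effect, the rejection rate is 0.044 with no such cases and 0.047 with 10% in both arms.

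**The case against.** The handling is a pre-specified intercurrent-event strategy, and several rules already limit the harm.

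- A recorded death by Day 28 removes the event.
- The freeze cannot create a gain that was not already present at discharge.
- A participant for whom invasive ventilation is medically indicated but not used scores 5, and one off oxygen with saturation at or below 93% scores 3.
- Participants who have not withdrawn consent get a Day 28 call recording vital status, and Protocol 7.3 has sites seek vital status from public sources as well. Apart from failed tracing, an unrecorded death needs consent withdrawal, after which vital status is not collected.
- Rule 1 protects the analysis in one respect: it stops a hospice discharge from becoming category 1.

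Most of this stands, and it makes the route narrow. It does not close it. The saturation rule blocks a baseline-4 participant, who needs category 2, but not a baseline-5 participant, for whom category 3 is already a two-category gain. The documents do not say how the medical-indication question on ventilation is answered once care is palliative. A participant alive in hospice at Day 28 is not caught by any of these rules.

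A reader might infer that participants sent home to die are counted as recovered. The documents do not support that: home and hospice/palliative are separate codes, and a recorded death by Day 28 is never an event. A reader might also infer that hospice handling makes one person improved on one key secondary and dead on the other. The pairing is real: a participant who discontinues with a score above 1 "will be considered as death on day 28" for mortality, while an earlier improvement is kept. But it follows from the general discontinuation rules in SAP 5.3.2 and arises equally for someone who discontinues from an ordinary ward.

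**Conclusion.** The point holds within limits. Under SAP 5.2.1 rule 1, a participant holding a gain of at least two categories at hospice or palliative discharge counts as a success on the primary endpoint and the Day 28 improvement key secondary, if alive at Day 28 or if a death goes unrecorded after discontinuation.

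Cases should be few. Within an arm each one raises the apparent improvement rate. It would be wrong to read this as bias towards sirukumab: cases in control shrink the contrast and cases in sirukumab enlarge it. If they are balanced, the illustration shows a modest loss of power and no visible change in type I error. The large shifts, to 0.60 or 0.91, need an assumed 20% in one arm only, although in control that is only about two participants.

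These sizes rest on assumed hospice fractions, the SAP's design assumptions and an unstratified test. The scoring result itself rests only on the rules as written. The change is worth making because it is cheap and aligns the endpoint with its intended meaning.

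**What to change.** Keep hospice/palliative discharge in rule 1 and add an override to SAP 5.2.1, 5.2.2, 5.2.3, 5.3.2 and Attachment 3:

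- Discharge to hospice or palliative care (code 7) by Day 28 is not sustained clinical improvement, whatever the category at discharge.
- In the primary analysis, censor at Day 28.
- In the Day 28 improvement key secondary, score as failure.
- Apply the same override to the one-category improvement endpoints in 5.4.1, where a smaller gain at discharge is enough.
- Report the number of such discharges by arm.

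Do not simply delete hospice from rule 1. These participants would then fall under rule 4 or 5 and become category 1 soon after discharge. The mortality key secondary would count them as alive if no death were reported (5.3.2), time to hospital discharge would count an event (5.4.1), and the one-category endpoints and the proportional odds model (5.4.2) would credit them with the best category.

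The cost is SAP wording and a small programming change. The destination code is already collected, and Protocol 9.4 places SAP finalization before database lock for the primary analysis. The improved-yet-dead inconsistency for participants who discontinue with a score above 1 needs its own correction in 5.3.2; this change does not resolve it.

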8.1.1. Six-point Ordinal Clinical Recovery Scale

The 6-point ordinal clinical recovery scale provides 6 mutually exclusive conditions ordered from best to worst, and the score reflects the participant's worst situation on the day assessed. The sponsor will assign the ordinal scale category based on the assessment of the participant's clinical status by the investigator. The ordinal clinical recovery scale categories are defined below.

Ordinal Clinical Recovery Scale (and Definitions)^a

1. Not hospitalized^b

Any of the following:

- Discharged from the hospital the day of assessment
- Hospitalized at the day of assessment but ready for discharge on the day of assessment, as judged by the investigator (eg, if still hospitalized in case of lack of bed availability in a skilled nursing facility, lack of social support at home).

2. Hospitalization, not requiring supplemental oxygen

^a Alternate care settings delivering care which would normally be delivered in a hospital setting will be categorized as hospitalized.

If a participant was discharged from the hospital “Against Medical Advice” on the day prior to the day of assessment, the participant will be categorized per the definitions above in the category the participant was in at the moment of discharge “Against Medical Advice”. The hospital recovery scale category will be considered missing on subsequent days.

If a participant declines medically-indicated mechanical ventilation, the participant will be categorized according to the care they would otherwise have received on that day.

^b A distinction will be made between participants discharged and in need of (score 1.2) or not in need of (score 1.1) oxygen supplementation as indicated by the investigator on the discharge questionnaire. This distinction will not be made when calculating improvements on the CRS, for which score 1 will be used in both cases.

3. Hospitalized, requiring low flow supplemental oxygen

- Hospitalized on the day of assessment (including readmittance), and supplemental oxygen is required by the participant.

Requiring supplemental oxygen is defined by:

- Receiving supplemental oxygen for instance through a face mask or nasal cannula, at a $\text{FiO}_2 < 50\%$,^a and not being able to sustain a blood oxygen saturation of $>93\%$ when breathing room air.

OR

- Not receiving supplemental oxygen and having a blood oxygen saturation of $\leq 93\%$ sustained for 5 minutes.

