 - Receiving supplemental oxygen (through a face mask, nasal cannula, high flow nasal canula or other where FiO2 is $< 50\%$) & the patient was not able to sustain a blood oxygen saturation of $> 93\%$ when breathing room air:
 - If assessed for blood oxygen saturation when breathing room air, SpO2 value should be $\leq 93\%$
 - If not assessed for blood oxygen saturation when breathing room air (for any reason), SpO2 value is assumed to be ≤ 93
 - OR
 - Not on supplemental oxygen and the minimum of all measured SpO2 values during the day $\leq 93\%$ (as this will be measured at least 4 times/day)
- **Score 2:**
 - Hospitalized according to hospitalization rules as discussed earlier.
- **Score 1:**
 - Not hospitalized, including subjects on low level of oxygen.

A distinction will be made between subjects discharged and in need of (score 1.2) or not in need of (score 1.1) oxygen supplementation as indicated by the investigator on the discharge questionnaire. This distinction will not be made when calculating improvements on the CRS, for which score 1 will be used in both cases.

Some examples

Case 1: Discharged from hospital on Day 6 (Rule 5)

| Case 1 | Day 3 | Day 4 | Day 5 | Day 6 | Day 7 | Day 8 to Day 28 |
|-------------------------|--------------|--------------|--------------|------------|-------|-----------------|
| Against medical advice? | | | | --/No | | |
| Status (SS*) | hospitalized | hospitalized | hospitalized | Discharged | | |
| Discharged to** | | | | 1/5/.. | | |
| ready (SS*) | --/Not ready | --/Not ready | --/Not ready | --/Ready | | |
| CRS | >1 | >1 | >1 | >1 | 1 | 1 |

Case 2: Alternate care setting (rule 1): hospitalized until Day 28

| Case 2 | Day 3 | Day 4 | Day 5 | Day 6 | Day 7 | Day 8 to Day 28 |
|-------------------------|--------------|--------------|--------------|------------------------|-------|-----------------|
| Against medical advice? | | | | --/No/YES | | |
| Status (SS*) | Hospitalized | hospitalized | hospitalized | Discharged | | |
| Discharged to** | | | | 2/3/.. | | |
| ready (SS*) | --/Not ready | --/Not ready | --/Not ready | --/Ready/ Not ready | | |
| CRS | >1 | >1 | >1 | >1 | >1 | >1 |

Case 3: Against medical advice (rule 2): hospitalized on Day 6 and 7, missing thereafter

| Case 3 | Day 3 | Day 4 | Day 5 | Day 6 | Day 7 | Day 8 to Day 28 |
|-------------------------|--------------|--------------|--------------|------------------------|-------|-----------------|

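### Discharge to a long-term, rehab or other facility is scored as category 1 whatever respiratory support the participant leaves on, so someone still at category 4 or 5 can count as a sustained improver

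*SAP*

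**What the plan says.** SAP 5.2.1 (Hospitalization status) lists five rules, applied in order: "Once a participant fulfils the criteria, the hospitalization status is defined and the evaluation stops".

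- **Rule 1.** "If a participant is discharged to the alternate care settings ‘different hospital’, ‘acute care facility’, ‘subacute care facility’ or ‘hospice/palliative discharge", the participant stays hospitalized, in the category held at discharge, until Day 28 or trial discontinuation. In Attachment 3 these four destinations are codes 2, 3, 4 and 7.
- **Rule 2** (against medical advice). The discharge category is kept for the day of discharge and the day after. Then: "The CRS will be considered missing from 2 days after discharge onwards".
- **Rule 4** (discharged although not ready). The participant is non-hospitalized from two days after discharge.
- **Rule 5** (any other discharge). "If a participant is discharged from the hospital, the day of discharge will be considered as" hospitalized. "After this day, the participant will be considered “Not hospitalized” until day 28 or trial discontinuation, whichever comes first".

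The destination codes in Attachment 3 also include "5=Long-Term Facility; 6=Rehab Facility; 7=Hospice/Palliative Discharge; 8=Other". Codes 5, 6 and 8 are not on the rule 1 list. The first worked example, "Case 1: Discharged from hospital on Day 6 (Rule 5"), uses home or code 5 as the destination and gives CRS 1 on Day 7 and on Days 8 to 28. It does not refer to oxygen or ventilation.

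Protocol 8.1.1, footnote a, says: "Alternate care settings delivering care which would normally be delivered in a hospital setting will be categorized as hospitalized". SAP 5.2.1 itself describes category 1 as taking in people on a low level of oxygen. Scores 1.1 and 1.2 are pooled when improvement is calculated.

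**The concern.** The protocol decides hospital status by the care a setting delivers. The SAP decides it by a list of destinations, and three destination codes fall outside that list. Every participant in the Primary analysis set starts at category 4 or 5 (SAP 2.2.3), and improvement needs two categories (SAP 5.2.1). Someone transferred to a long-term ventilator unit recorded as code 5 would move from category 5 to category 1 on paper without any clinical change.

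The data cannot easily correct this. Daily oxygen-type and FiO2 records run only to discharge (protocol 1.3 and 4.1). The later calls ask for oxygen need as yes or no (protocol 8.2.7). The SAP's definition of sustained improvement requires only that no loss be documented.

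At stake is the validity of the event on the primary endpoint and on the first key secondary endpoint: a participant who has not been weaned would be recorded in the best category.

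**Working it through.** **1. Apply the rules.** Take a participant discharged on Day 6 at category 4 or 5:

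| Destination and status | Day 6 | Day 7 | Days 8 to 28 |
|---|---|---|---|
| Codes 2, 3, 4, 7 (rule 1) | 4 or 5 | 4 or 5 | 4 or 5 |
| Codes 5, 6, 8, ready or blank (rule 5) | 4 or 5 | 1 | 1 |
| Codes 5, 6, 8, not ready (rule 4) | 4 or 5 | 4 or 5 | 1 |
| Codes 5, 6, 8, against medical advice (rule 2) | 4 or 5 | 4 or 5 | missing |

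If the discharge category equals baseline, the recorded change under rules 4 and 5 is 4 − 1 = 3 or 5 − 1 = 4 categories. Under rule 1 it is 0. The event stands unless the participant dies by Day 28 (SAP 5.2.3 then censors at Day 28) or a loss, such as a readmission, is documented.

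**2. Reproduce the plan's figures.** Inputs from SAP 1.4: 74 and 37 participants; survivors' time to improvement lognormal with medians 16.8 and 28 days and log-SD 0.9; mortality 20% and 40%. A simulated unstratified log-rank test (5% two-sided, 4,000 runs) gives 81.6% power, in line with the stated minimum of 80%.

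For the first key secondary endpoint (55% vs 30%, 1-sided 5%), use

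power = Φ[(d − 1.645·SE0) / SE1],

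where SE0 uses the pooled proportion and SE1 the separate proportions. Here d = 0.25, pooled p = (74×0.55 + 37×0.30)/111 = 0.467, SE0 = 0.1004 and SE1 = 0.0950. Power is Φ(0.893) = 81.4%.

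**3. Size of one case.** Expected improvers are 74×0.55 + 37×0.30 = 40.7 + 11.1 = 51.8. One case is 1/51.8 = 1.9% of events. It adds 1/37 = 2.7 points to the control rate, or 1/74 = 1.35 points to the sirukumab rate.

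**4. Effect on first key secondary power.** The case counts are assumptions; the documents give none.

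| Added cases (active, control) | Rates | Power |
|---|---|---|
| 0, 0 | 55.0% vs 30.0% | 81.4% |
| 2, 1 (equal rates) | 57.7% vs 32.7% | 81.0% |
| 4, 2 (equal rates) | 60.4% vs 35.4% | 80.8% |
| 0, 1 | 55.0% vs 32.7% | 72.5% |
| 0, 2 | 55.0% vs 35.4% | 62.2% |
| 2, 2 | 57.7% vs 35.4% | 72.2% |
| 1, 0 | 56.4% vs 30.0% | 84.9% |

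The 2, 2 row is not balanced. Under 2:1 allocation it misclassifies 5.4% of controls and 2.7% of the sirukumab arm.

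**5. Effect on the primary endpoint.** In the same log-rank simulation (2,500 runs), assume that the same share of surviving non-improvers in each arm becomes an event between Days 10 and 28. For shares of 10%, 30% and 50%, power is 79%, 77% and 75%.

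**The case against.** **Worst-first scoring.** Categories are checked from 6 down to 1. The criteria under categories 5 and 4 do not themselves test for hospitalization, so a ventilated participant might be said to stay at 5. The intent may well be that. But both headings say hospitalized, Attachment 3 takes score 5 from the oxygen-supplementation page, which is completed only while in hospital, and the worked example returns 1 with no oxygen check. As specified, the derivation gives 1.

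**Coding.** A site could record a ventilator unit as an acute or subacute facility, which rule 1 covers. The SAP is also to be read with the protocol, and the sponsor assigns the category. That may make cases rare or absent. It does not make the rule correct for those coded 5, 6 or 8.

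**The protocol also scores discharge as 1.** It does, without an oxygen condition, and rule 5 is a day stricter. Facility discharge in itself is therefore not the problem. The conflict is confined to facilities giving hospital-type care, which footnote a treats differently.

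**Sensitivity analyses.** Those planned for the primary endpoint are covariate adjustment and a survivors-only repeat, and neither rescores these participants. CRS (As observed) also gives score 1 when the participant is reported as not hospitalized.

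**Direction and size.** A reader might infer that affected participants gather in the slower-recovering arm, so that the rule hides a benefit and cuts power to between 62% and 73%. The documents do not support this. Those figures need an excess among controls, and an arm with fewer deaths could equally hold more ventilated survivors. This objection stands in full.

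**Conclusion.** The scoring error holds on the text. Rules 4 and 5 give CRS 1 to a participant who leaves at category 4 or 5 for code 5, 6 or 8. If that participant is alive at Day 28 with no documented loss, sustained improvement is recorded on the primary and first key secondary endpoints. This conflicts with protocol 8.1.1 footnote a and with the SAP's own description of category 1.

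Two broader readings are not supported. It is not true of every such discharge from the next day: participants judged not ready reach CRS 1 a day later, and discharges against medical advice become missing. Nor is the event irreversible, because death by Day 28 or a documented readmission can remove it.

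The number affected is unknown and could be zero. Each case is about 2% of expected events. First key secondary power is nearly unchanged at equal rates (about 81%) and moves either way when rates differ (72.5% with one extra control case, 84.9% with one extra active case). The finding is therefore misclassification of unknown direction on the primary outcome, and it should be corrected before the primary database lock. A loss of power has not been demonstrated.

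**What to change.** Reconcile the rule 1 destination list with protocol footnote a. Add to rules 4 and 5 in SAP 5.2.1, and to Attachment 3: a participant discharged to code 5, 6 or 8 whose CRS category at discharge is 4 or 5 is handled as under rule 1, with that category carried to Day 28 or trial discontinuation. Add a worked example for this case, and limit Case 1 to discharge categories 2 and 3 when the destination is code 5. Leave rule 3 and discharge home unchanged, since the conflict shown does not extend to them.

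The cost is SAP wording and one programming condition. It uses the oxygen type and FiO2 already collected for the day of discharge and can be specified without unblinding. There are two downsides. A participant who weans soon after transfer is scored conservatively, as rule 1 already does for other facilities. And because the score is the worst of the day, someone whose FiO2 reached 50% only once on the day of discharge would be held at category 4.
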